4. LIST OF ABBREVIATIONS AND DEFINITIONS OF TERMS

The following abbreviations and specialist terms are used in this study protocol.

| Abbreviation | Definition |
|--------------|---|
| AD | Alzheimer's disease |
| AE | adverse event |
| DEC | Dose Evaluation Committee |
| ECG | electrocardiogram |
| eCRF | electronic case report form |
| EEG | electroencephalogram |
| GCP | Good Clinical Practice |
| GMP | Good Manufacturing Practice |
| ICF | informed consent form |
| ICH | International Council for Harmonisation of Technical Requirements for Pharmaceuticals for Human Use |
| IEC | independent ethics committee |
| IP | investigational product |
| IRB | institutional review board |
| MCI | mild cognitive impairment |
| MRI | magnetic resonance imaging |
| NMDA | N-methyl-D-aspartate |
| PET | positron emission tomography |
| | |
| QTcF | QT interval corrected according to Fridericia's formula |
| SAE | serious adverse event |
| SAP | statistical analysis plan |
| SUSAR | suspected unexpected serious adverse reaction |
| TEAE | treatment-emergent adverse event |

5. INTRODUCTION

Diminished ability to learn and remember new information is the clinical hallmark of Alzheimer's disease (AD) and is associated with decreased quality of life and impaired functioning. Primary memory impairment tends to be followed by functional decline in networks that promote language, attention, executive functions, and visuospatial abilities (Weintraub 2012). SAGE-718 is hypothesized to correct disruptions in these large-scale neuroanatomical networks through positive allosteric activity at N-Methyl-D-aspartate (NMDA) receptors.

A subtype of glutamate receptors, NMDA receptors have a fundamental and well-documented role in regulating synaptic strength, health, and plasticity. The NMDA receptor antagonist memantine is approved as a treatment for AD, targeting glutamate excitotoxicity in later stages of the disease. However, blockade of NMDA receptor signaling can result in impaired neuroplasticity and cognitive deficits (Molinuevo 2005). Administration of a short-term NMDA partial agonist (D-cycloserine) in a small study of AD patients improved their scores on the cognitive subscale of the Alzheimer's Disease Assessment Scale, suggesting that NMDA-enhancing agents can benefit cognition in AD (Tsai 1999).

SAGE-718 is a novel, oxysterol-based, positive allosteric modulator of NMDA receptors that modulates the response to endogenous glutamate (Paul 2013). SAGE-718 only affects receptor function in the presence of endogenous glutamate, thus it does not directly activate the receptor and is not expected to cause glutamatergic excitotoxicity. SAGE-718 has been well tolerated in both healthy participants and a small cohort of Huntington's disease participants in previous clinical studies. However, based on nonclinical findings, the US Food and Drug Administration imposed a maximum median concentration (C_{max}) cap of 45 ng/mL. To date, clinical studies have used doses that resulted in exposures within this cap; neither serious adverse events (SAEs) nor AEs leading to discontinuation have been reported. A once-daily 3-mg dose of SAGE-718 is not predicted to exceed a median C_{max} of 45 ng/mL. For additional information on exposure caps, see the SAGE-718 Investigator's Brochure.

A direct correlation between SAGE-718 Oral Tablet exposure and fat intake has been observed in healthy adults, with significantly lower exposure in fasting participants than in the same participants after moderate and high fat-containing meals. Additionally, as fat levels increased, exposure variability decreased, allowing for more predictable C_{max} levels. Thus, in this study SAGE-718 will be administered after consumption of a morning meal containing approximately 30 g of fat. Based on the data from healthy participants, this regimen is projected to produce a median C_{max} of approximately 35 to 40 ng/mL at steady state.

[figure not shown]
The safety, tolerability, and of SAGE-718 Oral Tablet will be evaluated in this open-label study in individuals meeting diagnostic criteria for mild cognitive impairment (MCI) or mild dementia due to AD with otherwise stable neuropsychiatric symptoms. Additional data on the effects of SAGE-718 will be collected throughout, including assessments of

6. STUDY OBJECTIVES AND ENDPOINTS

6.1. Study Objectives

6.1.1. Primary Objective

The primary objective of this study is to evaluate the safety and tolerability of orally administered SAGE-718 in participants with MCI or mild dementia due to AD

6.2. Endpoints

6.2.1. Primary Endpoint

• Incidence of treatment-emergent adverse events (TEAEs)

6.2.2. Secondary Endpoint

• Change from baseline in vital signs, clinical laboratory analytes, electrocardiograms (ECGs), and responses on the Columbia–Suicide Severity Rating Scale (C-SSRS)

7. INVESTIGATIONAL PLAN

7.1. Overall Study Design

This is an open-label study evaluating the safety and tolerability of SAGE-718 and its effects in participants with MCI or mild dementia due to AD. Eligible participants will have a confirmed diagnosis of MCI or mild dementia due to AD, according to the National Institute on Aging-Alzheimer's Association 2011 diagnostic guidelines, which will be confirmed via the Clinical Dementia Rating Dementia Staging Instrument® (CDR). Participants will self-administer 3.0 mg of SAGE-718 once daily in the morning for 14 days within 1 hour after initiating a meal containing approximately 30 g of fat. Dosing and morning food intake will be tracked in a participant diary. Assessments will be performed as outlined in the Schedule of Assessments (Table 2)

At any time during the study, Sage may elect to form a Dose Evaluation Committee (DEC). If convened, this DEC will review the available data and provide recommendations for adjusting

the dose, administration schedule, and/or food intake and make adjustments for subsequent participants, if appropriate (see Section 7.4.2).

In the setting of public health advisories related to COVID-19, assessments scheduled to be conducted at the study site may be performed via telephone/video if feasible. For assessments that cannot be conducted by phone or video, an in-home visit may be conducted.

7.1.1. Screening Period

The Screening Period will begin with the informed consent process for prospective participants, including study partners. Subsequent screening assessments will be performed between Day -21 and Day -8 to determine eligibility, including but not limited to: assessments of vital signs, clinical laboratory tests, electrocardiogram (ECG), magnetic resonance imaging (MRI) of the brain, and C-SSRS. An electroencephalogram (EEG) will also be performed for all participants during Screening.

7.1.2. Baseline Period

The Baseline Period will occur from Day -7 through Day -1. During this period, each participant will receive dietary counseling to aid in choosing a morning meal containing approximately 30 g of fat to consume prior to dosing. On Day -7 (±1 day), participants will visit the clinic for confirmation of continued eligibility and collection of baseline safety data.

Additionally, participants will be trained on the use of a mobile data capture device Participants will continue to complete these assessments daily during the Baseline Period, using the mobile device remotely (at home), with the support of a study partner. On Day -1, participants will return to the study site for confirmation of continued eligibility and collection of further baseline safety data.

7.1.3. Treatment Period

Beginning on Day 1 and continuing through Day 14, participants will self-administer 3.0 mg of SAGE 718 (as six 0.5-mg oral tablets), once per day in the morning within 1 hour after initiating a meal containing approximately 30 g of fat, in accordance with the guidelines provided in a nutritional information brochure. During this period, participants will continue to complete daily assessments via mobile device either remotely (at home) or in the clinic (at scheduled clinic visits) and will track investigative product (IP) dosing and predose food intake in a participant diary.

On Day 1, Day 7 (±1 day), and Day 14, participants will arrive at the clinic in the morning prior to IP dosing and completion of daily mobile device tasks. Following predose procedures (ie, body weight, vital signs, ECG, followed by blood and urine collection for clinical laboratory analyses,

participants will eat a morning meal, then take the IP and complete the mobile device tasks under staff supervision.

At scheduled clinic visits during the Treatment Period, study staff will dispense a sufficient amount of SAGE-718 for daily administration until the next scheduled study visit. In addition to the clinic visits, study staff will contact participants by telephone on Day 4 to document any TEAEs and/or changes in concomitant medications.

7.1.4. Follow-up Period

Study staff will contact participants by telephone on Day 21 (± 1 day) to document any TEAEs and/or changes in concomitant medications. Participants will return to the clinic on Day 28 (± 2 days) for a follow-up visit.

7.2. Number of Participants

Up to 22 participants are planned to be dosed to obtain up to 20 participants that complete 14 days of dosing in this study. Additional participants may be dosed if the early discontinuation rate is greater than 10%.

7.3. Treatment Assignment

In this open-label study, all participants will receive 3.0 mg of SAGE-718 once daily for 14 days.

7.4. Dose Adjustment Criteria

Dosing may be interrupted in an individual participant due to an AE considered by the investigator to be related to IP, however, no individual dose reductions will be permitted.

7.4.1. Stopping Criteria

If clinical events suspicious for seizure occur after Screening, an unscheduled EEG will be performed for review by an independent epileptologist to identify evidence of seizure activity (see Section 12.1.6). Should the independent epileptologist identify evidence for a subclinical or clinical seizure, dosing with SAGE-718 will be stopped for that participant.

7.4.2. Dose Evaluation Committee

At any time during this study, Sage may elect to form a DEC (preferably after at least 5 participants have completed 14 days of dosing). If convened, this DEC will be responsible for reviewing the available data and providing recommendations for adjusting the dose, administration schedule, or food intake recommendations for subsequent participants. The DEC will include, at a minimum, the Sage program medical lead, a Sage Drug Safety and Pharmacovigilance physician, and a clinical operations representative and will be supported by a Sage biostatistician.

7.5. Criteria for Study Termination

Sage Therapeutics may terminate this study or any portion of the study at any time for safety reasons including the occurrence of AEs or other findings suggesting unacceptable risk to participants, or for administrative reasons. In the event of study termination, Sage Therapeutics will provide written notification to the investigator. Investigational sites must promptly notify their institutional review board (IRB)/independent ethics committee (IEC), where required, and initiate withdrawal procedures for participating participants.

8. SELECTION AND WITHDRAWAL OF PARTICIPANTS

8.1. Participant Inclusion Criteria

To be eligible to enroll in this study, participants must:

- 1. Be capable of providing informed consent
- 2. Have signed an informed consent form prior to any study-specific procedures being performed
- 3. Be willing and, in the opinion of the investigator, able to comply with study procedures
- 4. Be between the ages of 50 and 80 years, inclusive, at Screening
- 5. Meet the following criteria for MCI or mild dementia due to AD at Screening:
 - a. A memory complaint reported by the participant or his/her study partner
 - b. A CDR score of 0.5 to 1.0 (inclusive) with a memory box score \geq 0.5
 - c. Essentially preserved activities of daily living, in the opinion of the investigator
 - d. Brain magnetic resonance imaging (MRI) report, obtained within the 2 years preceding the Baseline Period, that is consistent with the diagnosis of AD-MCI with no clinically significant findings of non-AD pathology that could account for the observed cognitive impairment
- 6. Have a score of 15 to 24 (inclusive) on the Montreal Cognitive Assessment at Screening
- 7. Have an estimated premorbid IQ ≥85 (as assessed by the Test of Premorbid Functioning, performed at Screening)
- 8. Have a study partner who is reliable, competent, at least 18 years of age, willing to be available to the study center by phone, support study-specific activities, and accompany the participant to study visits as needed
- 9. Be ambulatory (use of assistance devices such as a walker or cane is acceptable; individuals requiring a wheelchair are excluded), able to travel to the study center, and in the opinion of the investigator likely to be able to continue to travel to the study center to complete study visits for the duration of the study
- 10. Have stable concomitant medication usage per the following criteria:
 - a. For psychotropic medications, including acetylcholinesterase inhibitors and other medications that are likely to have an effect on cognitive performance, the dose and frequency must remain stable for at least 12 weeks prior to the first IP administration and be expected to remain stable for the duration of the study
 - b. For all other concomitant medications, the dose and frequency must remain stable for at least 4 weeks prior to the first IP administration and be expected to remain stable for the duration of the study
- 11. Agree, if female, to use an acceptable highly effective method of contraception (as defined in Section 9.2.4) during participation in the study and for 30 days following the last dose of IP, unless she is postmenopausal (defined as no menses for 12 months

- without an alternative medical cause and confirmed by follicle stimulating hormone >40 mIU/mL), surgically sterile (hysterectomy or bilateral oophorectomy or bilateral salpingectomy), or does not engage in sexual relations which carry a risk of pregnancy
- 12. Agree, if male, to use an acceptable method of highly effective contraception (as defined in Section 9.2.4) during the 14-day Treatment Period and for 2 weeks after receiving the last dose of IP, unless the participant does not engage in sexual relations that carry a risk of pregnancy
- 13. Agree, if male, to abstain from sperm donation during the 14-day Treatment Period and for 2 weeks after receiving the last dose of IP
- 14. Agree to refrain from drugs of abuse and alcohol for the duration of the study

8.2. Participant Exclusion Criteria

To be eligible to enroll in this study, participants must not:

- 1. Have participated previously in a clinical study of SAGE-718, or have used any other investigational drug, biologic, or device or have participated in a clinical drug, biologic, or device study within 30 days or 5 half-lives (whichever is longer) prior to Screening
- 2. Have a condition that precludes undergoing an MRI, in accordance with standard operating procedures at the imaging facility (eg, ferromagnetic metal in the body, claustrophobia), in a participant requiring MRI during screening
- 3. Have clinically significant comorbid medical conditions, a chronic condition that is unstable or requires more than 2 medications to be controlled, or be taking concomitant medications that, in the opinion of the investigator, may make the participant unsuitable for inclusion or have the potential to compromise safety and/or compliance with study requirements
- 4. Have any medical or neurological condition (other than AD) that might be contributing to the participant's cognitive impairment or history of cognitive decline
- 5. Have a history of brain surgery, deep brain stimulation, a significant head injury causing loss of consciousness greater than 30 minutes, or hospitalization due to a brain injury
- 6. Have a history, presence, and/or current evidence of a clinically significant intracranial abnormality (eg, stroke, hemorrhage, space-occupying lesion, or other non-AD pathology) that is likely to call into question a primary clinical diagnosis of AD
- 7. Have a history of possible or probable cerebral amyloid angiopathy, according to the Boston Criteria (Greenberg 1995)
- 8. Have a history of treatment with an anti-amyloid therapy (including biologics) without subsequent MRI demonstrating the absence of amyloid-related imaging abnormalities
- 9. Be receiving any of the following prohibited medications:
 - a. Medications with potent effects at the NMDA receptor, including amantadine, ketamine, cycloserine, or related compounds
 - b. Memantine within the 4 weeks prior to IP administration

- c. Medications that inhibit cholesterol absorption (eg, ezetimibe)
- d. Bile acid sequestrants (eg, colesevelam, colestipol, cholestyramine)
- e. Other medications given at doses or in combinations that are likely to have a deleterious effect on cognitive performance, as described in the 2019 American Geriatrics Society Updated Beers® Criteria for Potentially Inappropriate Medication Use in Older Adults (American Geriatrics Society 2019)
- f. Prescribed cannabis or other THC-containing substances
- 10. Have an alcohol or drug use disorder within the past 12 months, as per DSM-5 criteria
- 11. Have a history of seizures or epilepsy, with the exception of a single episode of febrile seizures in childhood
- 12. Have current or recent suicidality, defined as follows:
 - a. Suicidal ideation within the past month, as evidenced by a score of 4 (active suicidal ideation with some intent to act, without specific plan) or 5 (active suicidal ideation with specific plan and intent) on the C-SSRS during Screening or Baseline
 - b. Suicidal behavior within the past year, as evidenced by a "Yes" on any of the 5 C-SSRS Suicidal Behavior Items (actual attempt, interrupted attempt, aborted attempt, preparatory acts, or behavior) on the C-SSRS during Screening or Baseline
 - c. Participant presents a serious risk of suicide in the opinion of the investigator
- 13. Have any of the following clinically significant medical conditions:
 - a. Any clinically significant finding on 12-lead ECG during Screening or Baseline
 - b. Supine vital signs outside of the following ranges during Screening or Baseline; vital sign measurements may be repeated once for initial values outside these ranges:
 - Heart rate <50 or >100 bpm
 - Systolic blood pressure <100 or >160 mmHg
 - Diastolic blood pressure <60 or >100 mmHg
- 14. Have a history, presence, and/or current evidence of serologic positive results for HIV-1 or HIV-2
- 15. Have a positive pregnancy test or be lactating at Screening or Day -1
- 16. Be investigative site personnel, sponsor personnel, or an immediate member of their family (spouse, parent, child, or sibling whether biological or legally adopted)

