- k To confirm self-reported postmenopausal status in women only.
- 1 Serum pregnancy tests for all female participants at Screening; urine pregnancy tests will be conducted for all female participants who are not postmenopausal or surgically sterile at other scheduled time points.
- m To include testing for hepatitis B and C, HIV-1, and HIV-2
- n Only in participants without an MRI report obtained within the 2 years preceding the Baseline Period

- q Participants and study partners will be trained to use all study-related software and devices. Additional guidance will be provided on choosing a meal with approximately 30 g of fat.
- r Includes select tests of the tests are to be performed postdose during the Treatment Period and at approximately the same time of day (±2 hours) throughout the study.
- s Includes
- t Measures directed to study partners may be administered by telephone or in person.
- v Daily reminders will be sent to participants to complete assessments of within 1 hour following IP administration, either remotely (at home) or in the clinic during the Treatment Period (with observation by study staff during scheduled clinic visits).
- w On visit days during the Treatment Period, participants will self-administer IP in the clinic under the supervision of study staff after the predose assessments and consumption of a morning meal.
- x Study staff will dispense sufficient IP for daily dosing at home until the next scheduled visit (see Section 9.4).
- y On Days 7 and 14, participants will return used IP packaging and any unused IP for site staff to document.
- z At Screening, include all psychotropic medications used within 12 weeks of informed consent, any other medications and supplements taken within 60 days of informed consent, and all medication used to treat AD, regardless of timing. After Screening, all changes to any medication or supplements should be captured.

| 3. | TABLE OF CONTENTS, LIST OF TABLES, AND LIST OF FIGURES | |
|--------|--|----|
| 1. | TITLE PAGE | 1 |
| 2. | SYNOPSIS | 5 |
| 3. | TABLE OF CONTENTS, LIST OF TABLES, AND LIST OF FIGURES | 16 |
| 4. | LIST OF ABBREVIATIONS AND DEFINITIONS OF TERMS | 21 |
| 5. | INTRODUCTION | 22 |
| 6. | STUDY OBJECTIVES AND ENDPOINTS | 23 |
| 6.1. | Study Objectives | 23 |
| 6.1.1. | Primary Objective | 23 |
| | | |
| 6.2. | Endpoints | 23 |
| 6.2.1. | Primary Endpoint | 23 |
| 6.2.2. | Secondary Endpoint | 23 |
| | | |
| 7. | INVESTIGATIONAL PLAN | 24 |

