12.1.7. Laboratory Assessments

Blood and urine samples for clinical laboratory assessments will be collected. will be collected for hematology, biochemistry, coagulation, urinalysis, and serology at the time points detailed in Table 2 and Table 3.

During Screening only, samples for clinical laboratory assessments will be collected from participants when they are in a fasted state.

Analytes to be evaluated are summarized in Table 4.

Table 4: Summary of Clinical Laboratory Analytes

| Biochemistry | Renal Panel: glucose, calcium, phosphorus, blood urea nitrogen, creatinine, sodium, potassium, chloride, bicarbonate |
|--------------|---|
| | Hepatic Panel: albumin, ALT, AST, total bilirubin, direct bilirubin, indirect bilirubin, alkaline phosphatase, total protein, lactate dehydrogenase, gamma glutamyl transferase |
| | Other: triglycerides, cholesterol (LDL, HDL), creatine phosphokinase, thyroid stimulating hormone |

| Coagulation | activated partial thromboplastin time, prothrombin time, and international normalized ratio |
|------------------------------|---|
| Hematology | red blood cell count (RBC), hemoglobin, hematocrit, white blood cell count with differential, platelet count, and if RBC indices are abnormal, reflex RBC morphology is indicated |
| Urinalysis | protein, glucose, pH, blood, leukocytes, leukocyte esterase, urobilinogen, bilirubin, ketones, nitrite |
| Serology (screening only) | hepatitis B surface antigen, hepatitis C IgM antibody, HIV-1 antibody, HIV-2 antibody |

Follicle stimulating hormone testing will be conducted to confirm whether a participant with ≥12 months of spontaneous amenorrhea meets the protocol-defined criteria for being postmenopausal.

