**Table 4 Clinical Laboratory Tests** 

Hematology	Serum Chemistry	Urinalysis	Coagulation
Hematology Red blood cell count Hemoglobin Hematocrit White blood cell count with differential Platelet count Red Blood Cell Indices (MCV, MCH, MCHC) Reflex to Red blood cell morphology if indices are abnormal	Serum Chemistry  Alanine aminotransferase Albumin Alkaline phosphatase Aspartate aminotransferase Total bilirubin Direct bilirubin Indirect bilirubin Total protein Creatinine Blood urea nitrogen Creatine kinase Gamma-glutamyl transferase	Urinalysis pH  Protein Glucose Red blood cell Nitrite Leukocyte esterase Ketones Bilirubin Urobilinogen	Coagulation  Activated partial Thromboplastin time Prothrombin time International normalized ratio
apnormai		Urobilinogen	
	Thyroid stimulating hormone (TSH)		

If a normal range is provided for the parameter, out-of-range values will be flagged as low or high, where applicable, in the participant data listings

The number and percentage of participants with potentially clinically significant (PCS) values will be provided in separate displays in hematology, serum chemistry, and liver function tests provided for such occurrence by time point.

PCS values will be identified for specific laboratory parameters as outlined in Table 5.

Liver function tests will be monitored closely for PCS values, and will be summarized for occurrence any time post-baseline for the following parameters for these PCS thresholds (for conditions involving more than one parameter, the results need to be from the same timepoint):

Alanine Aminotransferase: >3xULN, >5xULN, >10xULN Aspartate Aminotransferase: >3xULN, >5xULN, >10xULN

Alanine Aminotransferase or Aspartate Aminotransferase: >3xULN, >5xULN, >10xULN

Alkaline Phosphatase: >1.5xULN, >2xULN

Total Bilirubin: >1.5xULN, >2xULN

Total Bilirubin > 2xULN **AND** (Alanine Aminotransferase or Aspartate Aminotransferase >3xULN)
Total Bilirubin >2xULN **AND** Alkaline Phosphatase >2xULN **AND** (Alanine Aminotransferase or

Aspartate Aminotransferase >3xULN)

Any lab results considered clinically significant by the investigator will be captured as adverse events, hence will show up in AE displays.

Pregnancy test results will be listed but not summarized.

Table 5 Potentially Clinically Significant Values for Specific Laboratory Parameters

Laboratory Parameter	Gender	Units	Criteria for PCS Values (Observed values)		
			High	Low	
Hematology					
Hemoglobin	Male	g/L	>185	<115	
	Female	g/L	>170	<100	

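### The SAP counts liver test values above threshold after baseline regardless of the baseline value, and the shift summary that would show this is missing

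*Protocol*

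**What the plan says.** **Counting rule.** SAP 16.2 singles out liver function tests for close attention. It says that potentially clinically significant (PCS) values "will be summarized for occurrence any time post-baseline for the following parameters for these PCS thresholds". The thresholds are >3, >5 and >10 × ULN for ALT and AST, and >1.5 and >2 × ULN for alkaline phosphatase and total bilirubin. Two further rows combine bilirubin with the transaminases, one of them also with alkaline phosphatase. SAP Table 5 repeats single liver thresholds in the same form. None refers to the participant's baseline.

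**Shift summary.** Protocol 13.6.2 commits to showing the shift in laboratory abnormality from baseline to after baseline, using the laboratory's normal ranges.

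**Entry.** Protocol 7.1.1 says screening assessments are done "to determine eligibility, including but not limited to: assessments of vital signs, clinical laboratory tests", followed by ECG, MRI and C-SSRS. The Screening serology draw covers "hepatitis B surface antigen, hepatitis C IgM antibody, HIV-1 antibody, HIV-2 antibody" (Protocol Table 4). Among the exclusions, serology appears once: "Have a history, presence, and/or current evidence of serologic positive results for HIV-1 or HIV-2". Exclusion 13 has an ECG item, "Any clinically significant finding on 12-lead ECG during Screening or Baseline", and vital-sign ranges, but no laboratory item. Exclusion 3 applies to people who "Have clinically significant comorbid medical conditions, a chronic condition that is unstable or requires more than 2 medications to be controlled". Protocol 12.1 has the investigator class each out-of-range laboratory value as clinically significant or not.

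**The concern.** Change in laboratory analytes is part of the secondary safety endpoint, and there is no comparator arm to show how often a raised liver test would appear without drug. Readers will go first to the table of liver values above threshold. If it mixes values that rose on treatment with values that were already high, it overstates what happened after dosing. With about 22 participants, one person changes a row from none to several percent. A shift summary would ordinarily alert the reader, and it was promised, but the SAP does not carry it through.

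**Working it through.** **1. How such a participant can enter.** The five assessments named in Protocol 7.1.1, set against the criteria in 8.1 and 8.2:

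| Screening assessment | Criterion that uses it |
|---|---|
| Vital signs | Exclusion 13b |
| ECG | Exclusion 13a |
| MRI | Inclusion 5d |
| C-SSRS | Exclusion 12 |
| Clinical laboratory tests (chemistry, hematology, coagulation, urinalysis) | None named |

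Of the four serology markers, HIV-1 and HIV-2 have a rule (exclusion 14); hepatitis B surface antigen and hepatitis C IgM antibody have none. Two other screening tests do feed criteria: FSH (inclusion 11) and the pregnancy test (exclusion 15). The gap is therefore limited to the routine panels and the hepatitis markers. Exclusion 3 and the Protocol 12.1 grading remove a finding judged clinically significant. A raised value or positive marker judged not clinically significant meets no named exclusion.

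**2. What the SAP outputs do with a fixed elevation.** Take a hypothetical participant with ALT at 4 × ULN on Day -1 (the last scheduled laboratory draw before dosing, hence baseline) and at Days 7 and 14:

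- Liver PCS row >3 × ULN, any time post-baseline: counted.
- Change from baseline by visit: zero.
- TEAE (Protocol 12.2.1, SAP 16.1): not one on its face, since nothing began or worsened after dosing.
- Shift in abnormality (Protocol 13.6.2): high at baseline, high after. This display is not in the SAP.

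**3. Is the shift table really absent?** SAP 16.2 describes observed values, change from baseline, out-of-range flags in listings and PCS counts, but no shift. The laboratory tables in Appendix F run from 14.3.3.1.1 to 14.3.3.3.2 without a break in numbering, and no title mentions a shift. SAP 6.1 declares three departures from the protocol (medication summary, medical history summary, Alzheimer's disease history); this is not one of them.

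**4. Comparison within the SAP.** Blood pressure (Table 6) and QTcF (Table 7) have separate change-from-baseline criteria beside the observed-value criteria. Among laboratory parameters only creatinine mentions baseline, as an alternative (>3 × ULN or >3 × baseline). The liver tests have no such element.

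**5. Size.** The denominator comes from Protocol 13.8: 20 completers at 10% dropout, approximately 22 dosed. Check: 20 × 1.10 = 22 and 20/0.90 = 22.2. The figure is reproduced and not in dispute.

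- One pre-existing, persistent elevation: 1/22 = 4.5% (exact 95% interval 0.1% to 22.8%); 1/20 = 5.0% among 20.
- Two: 2/22 = 9.1% (1.1% to 29.2%).
- For comparison, 0/22 has an exact 95% interval of 0% to 15.4%.

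**6. How likely is at least one?** The documents give no proportion p of entrants above a liver threshold at baseline, so p is an assumption. P(at least one of 22) = 1 − (1 − p)^22:

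| Assumed p | P(at least one) |
|---|---|
| 0.5% | 10.4% |
| 1% | 19.8% |
| 2% | 35.9% |
| 5% | 67.6% |

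These are chances of such a person being enrolled. The row is affected only if the value also stays above the threshold after dosing.

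**The case against.** The strongest case on the other side has four parts.

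- **Entry is guarded.** A reader might infer that known liver disease can enter freely. The documents do not support that: exclusion 3 bars clinically significant conditions, and Protocol 12.1 requires a judgement on every out-of-range value. ECG and MRI eligibility rest on similar judgement. This stands, and it narrows the entry gap to findings judged not clinically significant.
- **The data are visible.** A reader might infer that a pre-existing elevation could not be told apart from a drug effect. That is also too strong. Chemistry is drawn at Screening and Day -1, change from baseline is summarized by visit, and Listing 16.2.8.2 gives biochemistry with change from baseline. With about 22 people the pattern can be found line by line. This stands as mitigation, but the summary table itself would still mislead.
- **The primary endpoint is not shown to be affected.** An unchanged elevation is not a TEAE, and the SAP's label is potentially clinically significant values, not liver events. This stands.
- **Hepatitis status alone moves nothing.** A surface antigen carrier with normal transaminases adds to no liver row, and the documents reviewed identify no hepatic risk of the drug. Whom to exclude is the sponsor's decision, and Amendment 1 aimed to widen entry. This stands, so the eligibility text is a matter of reconciliation, not of a particular rule being wrong.

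None of this answers the counting rule or the missing shift summary.

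**Conclusion.** The point holds for the analysis. The liver PCS counts ignore baseline, so a persistent pre-dose elevation is reported as a post-baseline occurrence. The shift summary promised in Protocol 13.6.2 has dropped out of the SAP without being declared. Each affected participant adds 1/22 = 4.5% to a row, on the assumption that 22 are dosed and that the value was above the threshold before dosing and stays there. How often that would happen is unknown.

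On eligibility the finding is limited. Protocol 7.1.1 and the hepatitis serology imply a use at entry that section 8.2 does not state for the routine panels or the hepatitis markers. It would be wrong to read this as showing that no screening test other than HIV affects entry, or that the trial exposes people with clinically significant liver disease.

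This is a free improvement to the reporting of a secondary safety endpoint. It does not threaten the primary analysis.

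**What to change.** 1. **SAP 16.2 and the liver PCS display.** Beside each count, show how many of those participants were already above the same threshold at baseline. Alternatively, restrict each row to participants at or below the threshold at baseline and state that denominator. Cost: about one column in an existing table.
2. **SAP 16.2, Appendix F and 6.1.** Add the laboratory shift table promised in Protocol 13.6.2, or declare its omission in 6.1 with a reason. Adding it is preferable. It does not replace item 1: a normal-range shift shows that a participant was high at baseline, but cannot distinguish a value steady at 4 × ULN from one that rose to it from just above normal.
3. **Protocol 7.1.1, 8.2 and the synopsis.** Reconcile these by stating how the screening laboratory panels and the hepatitis B and C results bear on eligibility, including if they are collected for information only. The clinical rule is for the sponsor to set.

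Items 1 and 2 use values already scheduled for collection, need no new test, and remain useful if enrollment is complete. If the database is already locked, the SAP's own provision applies: describe and justify the change in the clinical study report. Item 3 is a text clarification; its effect on screen failures depends on the rule the sponsor states and cannot be estimated from the documents.
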